9.3 Populations for Analyses

All-treated population: Any subject randomized into the study that received at least one dose of study drug.

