- 3) Participants who successfully complete detoxification, will undergo a neuroimaging session immediately followed by induction to XRNTX or XRBUP over a period of up to 14 days, which will include oral Naltrexone 50 mg for the XRNTX group followed by the 1st injection of XRNTX, or by injection of one or more weekly XRBUP in 8mg, 16mg or 24 mg strength with the total weekly dose not to exceed 32mg, followed by an injection of monthly XRBUP in 64, mg, 96mg, or 128mg strength (**Figure 1**). If deemed clinically necessary, induction to XRBUP may be extended by up to one week, using the same weekly Bixadi schedule. Buprenorphine/naloxone (Suboxone) is an FDA-approved sublingual form of buprenorphine that may be used during the induction if clinically indicated. Total duration of induction onto XRBUP will not exceed 14 days. Participants who are unable to complete the detoxification or induction will be excluded from the study and referred to a clinical addiction program for continuation of treatment as indicated. Suspected adverse reactions to any of the medications used in the study will be reported appropriately to the IRB, FDA at [name] or www.fda.gov/medwatch, Alkermes, plc at [name] or email: [contact] or both or Braeburn Inc at [name] .

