The clinical management of XRBUP is similar to XRNTX except that induction to XRBUP requires partial detoxification followed a weekly dose of injectable XRBUP, while induction on XRNTX requires complete abstinence (Lofwall et al 2018). The goal of the detoxification and induction phase of the experiment is to establish a uniform starting point for both monthly formulations. To achieve it, we will detoxify all participants to abstinence and randomize after abstinence from illicit opioids has been achieved. Outpatient detoxification to abstinence takes between 5 and 10 days. Following detoxification, the XRBUP participants will receive a combination of 8mg, 16mg, and 24mg strengths of weekly XRBUP, not to exceed 32 mg/week, followed by the injection of 64mg, 96mg, or 128mg of monthly XRBUP. If clinically indicated, supplemental doses of sublingual buropenorphine/naloxone (Suboxone) may be used. If clinically indicated, the induction procedure may be extended by up to one week, using the same approach. The total duration of induction to Brixadi will not exceed 14 days. The XRNTX participants will receive 50 mg of oral naltrexone for 7-10 days after detoxification followed by the 1st XRNTX (380 mg naltrexone IM) injection. The use of symptom-driven titration of weekly XRBUP during induction reflects current best practices in administration of the drug and increases participant safety and comfort. The XRBUP induction period is also intended to synchronize the timepoint at which both cohorts begin their monthly treatments. The non-opioid detoxification will follow the procedure described in our previous neuroimaging studies (Langleben et al 2014, Langleben 2015, Wang et al 2018). Participants who are opioid-positive upon screening will undergo office-based withdrawal management (detox) by the study physicians using FDA-approved generic medications to alleviate opioid withdrawal symptoms following a symptom-triggered approach that includes clonidine 0.1 mg tid, dicyclomine 20 mg qid, clonazepam 0.5 mg q12 hrs PRN, diphenhydramine 25 mg PRN, non-steroidal anti-inflammatory medicines PRN, Trazodone 50 mg qhs and oral hydration solutions (Molenberghs et al 2005). The induction to XRNTX or XRBUP will commence immediately after the baseline MRI session. The 1st monthly injection will be administered by an experienced nurse practitioner after induction is completed (approximately 7-14 days later).

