9 STATISTICAL CONSIDERATIONS

9.1 Statistical Hypotheses

Overview of primary hypotheses: Our primary response will be a binary indicator of treatment failure on the XRNTX or XRBUP regimen, defined as ≥ 2 weekly UDS positive for opioids, or self-report of ≥ 2 periods of three or more days of opioid use, or refusing XRNTX or XRBUP, or dropping out of study entirely. In hypotheses H1a and H1b, we are examining the effects of small, pre-specified, sets of measures, so our analyses will focus on model fit and prediction, and not on model selection. In hypothesis H1c, we search for best sets of predictors among demographic and clinical-behavioral variables, and over sets of brain/neural measures, so our focus is on model selection and on avoiding overfitting to the available data.

R61 Phase:

Hypothesis H1 (fMRI): For each of the cue reactivity (H1a), response inhibition (H1b), and connectivity (H1c) brain measured, we have a small number of neural responses associated with one or two regions of interest. These variables are continuously distributed, so we will test Hypotheses 1a, 1b and 1c using a repeated measures analysis of variance (rm-anova). The models will include a within-subject factor for Session (PRE vs ON) and a between-subject factor Group (XRNTX vs XRBUP), and their interaction. To accommodate the anticipated non-normal distributions of the response, we will use a generalized estimating equation (GEE) approach, using robust standard errors, using a compound symmetry working correlation structure for the within-subject correlations between the PRE and ON fMRI scans (Diggle PJ et al 2002). We will perform the rm-anova separately for each ROI (mPFC and VS for H1a, IFC for H1b, and VS-rtIFG and VS-mPFC for H1c). The hypotheses will be addressed by the Session by Group interaction, and we will obtain estimates and standard errors of the PRE vs ON change within each of the two groups, along with the size, standard error and significance of the differences between these estimates.

Sample size considerations for sample: The sample size is adequate for application of the GEE methods to obtain robust standard error (Lipsitz et al 1994). For a test of the PRE vs ON effect, our sample yields 80% power for a one-sided test that the ON levels will be Cohen's $d=0.4$ lower than the PRE levels, consistent with a decrease of Cohen's $d=0.5$ observed in our preliminary data and a decrease of Cohen's $d=0.3$ in the Suboxone sample.

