Effects of neural response on relapse vulnerability: Our primary outcome combines adherence to treatment and frequency of illicit opioid use during treatment. The primary outcome is a binary indicator of treatment success: if a patient provides ≥ 2 weekly UDS positive for opioids, or self-report of \geq two or more periods of ≥ 3 days of opioid use, or refuses XRNTX or XRBUP, or drops out of treatment entirely, then they will be classified as a treatment failure; otherwise they will be classified as a treatment success. We will calculate the PRE-ON change in %-signal-change for each of the regions and neural responses described in the R61 phase. We will use logistic regression models to predict the log-odds of treatment success (Aitkin et al 2009). The predictors in the model will be a binary factor for Group (XRNTX vs. XRBUP), and the neural change scores. We anticipate that there will be some greater PRE to ON changes in the XRNTX group than in the XRBUP group, so there will be some confounding between the effects of change score and the effects of Group on the rates of positive UDS. Thus, we will include Group first in our model, so evaluating the Group effect separate from the change-score effects, and then include the change scores in a model including Group, so evaluating the additional effect of change-scores in addition to the existing effects of Group. To assess whether the effects of the change scores differ between the XRNTX and XRBUP groups, we will also test for interaction effects between Group and each of the change-scores, by adding the interaction terms to the model that includes the group and neural change score main effects. We will check the assumptions underlying the logistic regression models (e.g. linearity of covariates effects on log-odds, outliers, influential observations) using standardized residuals, influence diagnostics, and graphical displays.

Sample size considerations for the sample: Analyses of Session by Group effects on neural response: For a one-sided test that the PRE vs ON effect is larger in the XRNTX group than in the XRBUP group, our sample of 70 per group yields 81% power for an effect of $d=0.42$ or greater. This effect is similar to the effects observed in the preliminary data. On the basis of the preliminary data we anticipate Group by Session effects of approximately $d=0.38$ in the VS and $d=0.42$ in the mOFC.

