Analyses of effects of neural response on relapse vulnerability: We consider the effect for an individual neural change variable, in a model where Group is included, assuming a small effect for Group (odds ratio = 1.25). We have three domains, with two neural variables in two domains and one in the other, so we provide power for $\alpha=0.05$ and for $\alpha=0.025$. For $\alpha=0.05$ we have 80% power for an odds ratio of 1.75 or higher per standard deviation increase in a neural variable; for $\alpha=0.025$, we have 80% for an odds ratio of 1.86 or higher.

Analyses of polysubstance use outcomes: We will also examine the effects of Group and neural change variables on other substance use outcomes, including self-report and UDS measures of opioid, stimulant, and benzodiazepine use. Here, we will use the self-report and UDS measures to create binary weekly measures of use for each substance, and use GEE repeated measures logistic regression models, with Group and the neural change measures as predictors, to estimate and test effects. These secondary analyses will be subject to missing data. We anticipate 25% dropout rates. To assess possible effects of nonignorable missingness on inference, we will perform sensitivity analyses using pattern-mixture models and selection models. For pattern mixture models, subjects are grouped on the basis of their pattern of missing data, and the resulting categorical factor is included in the analyses as a main effect and interaction with predictors of interest. Overall predictor effects may be found by averaging over the patterns (Molenberghs et al 2005). Selection models (Molenberghs et al 2005) take a different approach, by explicitly modeling the probability of drop out, and incorporating the predicted probabilities into the main longitudinal analysis, with the dropout and response processes included in a single bivariate model. Comparisons between the predictions of the primary analyses, and each set of pattern mixture and selection models, provides some evidence for assessing the sensitivity of results to missing data.

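### The only analysis set requires a post-randomisation dose, so the Group-only step of the treatment-failure model may not compare the arms as randomised

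*Combined protocol and SAP*

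**What the plan says.** - **Analysis set.** Section 9.3 gives one population: "Any subject randomized into the study that received at least one dose of study drug". No intention-to-treat or all-randomised set is defined; the term intention-to-treat appears only in the abbreviation list.
- **Timing.** Section 6.1 states: "we will detoxify all participants to abstinence and randomize after abstinence from illicit opioids has been achieved". The Schedule of Activities (13.1) also places randomisation ahead of induction.
- **Induction by arm.** Section 2.3.1 describes "oral Naltrexone 50 mg for the XRNTX group followed by the 1st injection of XRNTX, or by injection of one or more weekly XRBUP". Section 6.1 gives 7 to 10 days of oral naltrexone before the first XRNTX injection.
- **Early losses.** Section 2.3.1: "Participants who are unable to complete the detoxification or induction will be excluded from the study". Section 7.2 allows replacement of randomised participants who do not receive the injection, without saying which injection.
- **Outcome.** The Section 9.1 overview counts as failure "or refusing XRNTX or XRBUP, or dropping out of study entirely". The Phase 2 text of 9.1 says that if a participant "refuses XRNTX or XRBUP, or drops out of treatment entirely, then they will be classified as a treatment failure".
- **Model.** Section 9.1: "Thus, we will include Group first in our model, so evaluating the Group effect separate from the change-score effects". The neural change scores are then added to the model that contains Group.

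**The concern.** Every dose in this trial is given after randomisation, and the first product differs by arm. Entry to the only analysis set therefore depends on an event that the assigned arm can influence. The outcome definition points the other way, since early refusal and dropout are meant to be informative failures.

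The analysis exposed is the Group-first step, which the plan includes in order to evaluate the Group effect on treatment success. If early losses leave unequally by arm, that estimate loses the protection of randomisation. The dropout models and the complier analysis in Section 9.4.1 do not restore people outside the set, and no all-randomised denominator is named for them.

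**Working it through.** **1. What the plan's figures say about loss.** Section 5.3 expects about 75% of 200 recruits to reach the first monthly injection and gives the count as 160. But 0.75 × 200 = 150, and 160/200 = 80%. Loss up to that injection is therefore 20% or 25%, and it includes detoxification failures before randomisation. No figure isolates loss after randomisation, so the true size cannot be derived.

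**2. Who is outside the set, by reading of *study drug*.**

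| Reading | Randomised participants outside the set |
|---|---|
| Any induction product counts, oral naltrexone included | Those who refuse or leave before the first induction dose |
| Extended-release injections only, weekly XRBUP included | XRNTX losses during the oral phase; XRBUP losses only before the first weekly injection |
| Monthly injections only | Induction losses in both arms |

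On every reading, someone who refuses before any dose is a failure under 9.1 and outside 9.3.

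**3. Illustration (all inputs assumed).** 90 randomised per arm; 20 lost in induction in total where both arms lose, leaving the 160 of Sections 5.3 and 9.2; failure share f = 0.50 among all randomised in both arms; every loss is a failure. The true odds ratio (OR) for failure, XRNTX v XRBUP, is 1. Successes stay at 45 per arm, because only failures are removed.

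With shares lN and lB removed from XRNTX and XRBUP, OR = (f − lN)/(f − lB).

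- Equal loss, 10 v 10: 35/80 v 35/80, OR 1.
- Unequal loss, 12 v 8: 33/78 = 42.3% v 37/82 = 45.1%, OR = 33/37 = 0.89. Reversing the arms gives 37/33 = 1.12.
- One-arm loss, 10 of 90 removed from XRNTX while XRBUP losses stay in: 35/80 = 43.8% v 45/90 = 50%, OR = 35/45 = 0.78.

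**4. Sensitivity of the one-arm case.** Here OR = 1 − lN/f. With 10 of 90 lost, f = 0.40 gives 0.72 and f = 0.60 gives 0.81. With 5 of 90 lost and f = 0.50, OR = 40/45 = 0.89. With no loss, OR = 1.

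**5. Rejection rates.** Exact enumeration of two binomials, two-sided 5% likelihood-ratio test (an assumed test; the plan sets no alpha for Group):

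| Case | Rejection |
|---|---|
| 90 v 90, no loss | 4.5% |
| 12 v 8 lost | 6.5% |
| 5 of 90 lost, one arm | 6.7% |
| 10 of 90 lost, one arm | 13.0% |

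**6. Yardstick.** The power text in 9.1 assumes a Group OR of 1.25. The one-arm case gives 1/0.78 = 1.29. The 1.25 is an assumed covariate effect in the power calculation for a neural variable, so it indicates scale only.

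**The case against.** Five points on the other side carry weight.

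- **Section 9.3 assigns its set to no named analysis.** A reader might infer that it governs the Group-first step. It does so only by default. Change scores need the Day 55 scan, so if the nested models share one sample, having the scan is the tighter restriction. This stands, but it moves the selection later and does not remove it.
- **Group is largely an adjustment term.** The H2a hypothesis concerns brain signal and its interaction with Group, and no alpha is set for Group. This stands and limits the consequence. The text still says that the Group effect will be evaluated.
- **The OR of 0.78 rests on the least-supported reading.** It needs weekly XRBUP to count as study drug, oral naltrexone not to count, and the exclusion in 2.3.1 not to remove XRBUP losses. The synopsis and the numbered injections in 13.1 lean towards monthly injections, where the rule is the same in both arms. This stands.
- **Failed induction is not explicitly a failure.** A reader might infer that the plan defines every induction loss as one. The wording covers refusal and dropout, and the 9.1 overview speaks of failure on the regimen. A participant whom the study excludes is a failure only by inference.
- **The adherence count of 1, 2 or 3 in Section 3.2.** A reader might see a conflict with 9.3. There is none on its face: a scale starting at 1 fits a dosed-only set.

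**Conclusion.** The concern holds as a conflict between the analysis set, the outcome definition and the handling of early losses, with one exposed estimate: the Group-only effect on treatment failure. In either the default set or the scan set, that estimate is conditional on post-randomisation events.

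Its size and direction are not known. Under the stated assumptions the OR is 1 with equal loss, 0.89 with 12 v 8, and 0.78 in the one-arm case. The last figure and its 13.0% rejection rate might be read as the expected bias. The documents do not support that, because both the loss and the reading of *study drug* are assumed.

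A reader might also infer that the fMRI Group by Session result would be put right by changing 9.3. It would not: that test and the change-score tests need the on-treatment scan and stay conditional on it.

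**What to change.** 1. Fit the Group-only treatment-failure model in all randomised participants by assigned arm, including any who are replaced, and count post-randomisation refusal, dropout and failed induction as failures.
2. Refit the Group-only model in participants with an on-treatment scan, as the base for the added change-score test, so that the nested models share one sample. State that this sample is conditional on completing induction and having the scan.
3. Reconcile Sections 2.3.1, 7.2, 9.1 and 9.3, including what *study drug* and *the injection* mean and whether exclusion means leaving participation or leaving the data.
4. Report induction loss by arm in the participant flow.

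The cost is wording, one extra model fit and one line in the flow diagram; there are no new visits. Reported success will look lower: with the equal-loss illustration it falls from 45/80 = 56.3% to 45/90 = 50% in each arm. The Group-only result will appear in two samples and needs a sentence to explain why.

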7.2 Participant Discontinuation/Withdrawal from the Study

Participants are free to withdraw from participation in the study at any time upon request.

An investigator may discontinue or withdraw a participant from the study for the following reasons:

- Pregnancy
- Significant study intervention non-compliance
- If any clinical adverse event (AE), laboratory abnormality, or other medical condition or situation occurs such that continued participation in the study would not be in the best interest of the participant
- If the participant meets an exclusion criterion (either newly developed or not previously recognized) that precludes further study participation
- Participant missing a due injection for more than 14 days.

The reason for participant discontinuation or withdrawal from the study will be recorded on the study Case Report Form (CRF) along with a note to file. Subjects who sign the informed consent form and are randomized but do not receive the injection may be replaced. Subjects

who sign the informed consent form and are randomized and receive the injection, and subsequently withdraw, or are withdrawn or discontinued from the study, will not be replaced.

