8.3.3.2 Relationship to Study Intervention

All adverse events (AEs) must have their relationship to injection assessed by the clinician who examines and evaluates the participant based on temporal relationship and his/her clinical judgment. The degree of certainty about causality will be graded using the categories below. In a clinical trial, the study product must always be considered.

- Related – The AE is known to occur with the injection there is a reasonable possibility that the injection caused the AE, or there is a temporal relationship between the injection and event. Reasonable possibility means that there is evidence to suggest a causal relationship between the injection and the AE.
- Not Related – There is not a reasonable possibility that the administration of the injection caused the event, there is no temporal relationship between the injection and event onset, or an alternate etiology has been established.

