Missing Data and Nonadherence: For the longitudinal analyses described above, premature discontinuation from treatment and occasional missing daily use indicators will lead to incomplete data. The mixed effects models described above can make use of all available data provided by subjects, but the inferences drawn from them will be unaffected by the missing data only if the missing data can be regarded as ignorable, in the sense of Laird ⁵⁵. To assess the sensitivity of our analyses to this assumption, we will use shared parameter models, which allow for correlated random effects underlying the cocaine use measurements and the pattern of dropout ⁵⁶. We will also use selection models to examine the effects of missing data ^{57,58}. We will explicitly model the probability of premature discontinuation at a time point as a function of baseline characteristics and responses at previous time points, using a logistic regression model, and incorporate the predicted probabilities into a weighted analysis of the main hypotheses. We will do analyses in a range of assumptions and assess the sensitivity of results to them ⁵⁸. We will use urine drug screens, record of clinic visits and receipt of injectable medications as measures of compliance with assigned medication regime. We will use the methods of Nagelkerke et al ⁵⁹ and Small et al ⁶⁰, to obtain estimates of the intervention effect in a population compliant with treatment i.e. the Complier Average Causal Effect (CACE).

Safety: The adverse event responses will be analyzed as a measure of safety. Total number of adverse events, adverse events leading to discontinuation (in the judgment of the study physician), % of patients reporting at least one adverse event, clinical lab assessments, vital signs and

evidence of clinical worsening (by urine drug screen results and TLFB results) will be considered in assessment of safety. In a manner parallel to the analysis for therapeutic response, medication group, gender, age and other clinical variables will be entered into a generalized linear mixed effects model to predict adverse events.

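### Relatedness and expectedness are judged against the injection, which leaves out the oral naltrexone induction in one arm, and the only analysis set leaves study drug undefined

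*Combined protocol and SAP*

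**What the plan says.** **Causality.** Section 8.3.3.2 states: "All adverse events (AEs) must have their relationship to injection assessed by the clinician". An event can be Not Related on any one of several alternatives, one of which is that "there is no temporal relationship between the injection and event onset". Section 8.3.3.3 judges expectedness against the risk information for the injection. Sections 8.3.4 to 8.3.6 use the wider term, study treatment.

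**Order of events.** Randomisation follows abstinence and precedes induction (Section 6.1 and the Schedule of Activities). Section 2.3.1 describes induction as "oral Naltrexone 50 mg for the XRNTX group followed by the 1st injection of XRNTX, or by injection of one or more weekly XRBUP". Section 6.1 gives the oral phase as 7-10 days, and the schedule puts Injection 1 at day 10.

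**Analysis set.** Section 9.3 defines one population: "Any subject randomized into the study that received at least one dose of study drug". Study drug is not defined. Section 7.2 adds: "Subjects who sign the informed consent form and are randomized but do not receive the injection may be replaced". For either arm, Section 2.3.1 says: "Participants who are unable to complete the detoxification or induction will be excluded from the study".

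**Safety analysis.** Section 9.4.1 plans the total number of adverse events, those leading to discontinuation and the percentage "of patients reporting at least one adverse event". It adds that "medication group, gender, age and other clinical variables will be entered into a generalized linear mixed effects model to predict adverse events". It names no analysis set and does not filter by relatedness.

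**The concern.** Section 2.2.1 names precipitated withdrawal, in someone not sufficiently detoxified, as the main potential side effect of both medications. One would expect it at first exposure to the assigned drug. In the XRBUP arm that exposure is an injection. In the XRNTX arm it is a tablet, taken a week or more before the first injection. A causality rule keyed to the injection therefore covers the critical period in one arm and not in the other.

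Two things are at stake. The first is the count of related events. Section 7.1 stops the study when serious or unexpected events attributed to study medication reach 10% of patients, so a misgraded serious reaction to oral naltrexone could be missed by that limb. The second is who is compared. If oral naltrexone is not study drug, the XRNTX participants who leave during induction, perhaps because of a reaction, are outside the analysis set, while their XRBUP counterparts are inside it.

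**Working it through.** The documents give no adverse event rate and no induction failure rate by arm, so there is no figure of the plan's to reproduce. The check is a reading of the text, followed by an illustration on assumed inputs.

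**Step 1: the relatedness rule, applied to one reaction in each arm.**

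| | XRBUP, after first weekly dose | XRNTX, on oral naltrexone |
|---|---|---|
| Injection already given? | Yes | No |
| Temporal link to an injection? | Yes, so Related | None, so the Not Related alternative is met |
| Relationship to study treatment (8.3.4)? | Yes | Yes, if oral naltrexone counts |

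The XRNTX grade depends on which section the clinician follows. This does not turn on what study drug means in Section 9.3.

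**Step 2: three readings of study drug in Section 9.3.**

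- *Any assigned induction medication.* Both arms enter at the first induction dose, and the set is even.
- *The extended-release products, weekly or monthly.* XRBUP participants enter at the first weekly injection. XRNTX participants enter only after the oral phase, so those who stop during it never enter.
- *Monthly products only.* Those who leave during induction fall out of both arms. The set is even, but the period of greatest interest is lost for them.

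The second reading is the likeliest. Sections 6 and 6.1.1, with Section 6.2, describe weekly and monthly XRBUP and the 380 mg naltrexone injection as the study medications, and do not list oral naltrexone. Section 3.1 names the interventions as XRNTX and XRBUP.

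**Step 3: possible size on the second reading.** Let f be the share of each randomised arm that leaves during induction after the first induction dose, a the adverse event risk in leavers and c the risk in completers, all equal between arms. Then

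- XRBUP risk = f × a + (1 − f) × c
- observed XRNTX risk = c, because its leavers are dropped
- spurious gap, XRBUP minus XRNTX = f × (a − c)

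Assumed: 80 randomised per arm (the group size in Section 9.2), c = 30%, a from 50% to 100%.

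| f | XRNTX participants dropped (80 × f) | of these with an event | gap, a = 50% | gap, a = 100% |
|---|---|---|---|---|
| 5% | 4 | 2-4 | 0.05 × 0.20 = 1.0 points | 0.05 × 0.70 = 3.5 points |
| 10% | 8 | 4-8 | 0.10 × 0.20 = 2.0 points | 0.10 × 0.70 = 7.0 points |
| 20% | 16 | 8-16 | 0.20 × 0.20 = 4.0 points | 0.20 × 0.70 = 14.0 points |

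If a = c, or if f = 0, the gap is 0. The value of f cannot be taken from Section 5.3, which expects about 75% to reach the first monthly injection. That loss includes people who never achieve abstinence and so are never randomised.

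**The case against.** The best reply is that this is loose wording, and that the documents can be read evenly. Section 9.3 does not mention injection. Section 2.3.1 makes oral naltrexone part of XRNTX induction. Section 3.2 counts interventions as one to three, which suggests the monthly injections. This stands as far as it goes: exclusion of oral-only participants is the likelier reading of Section 9.3, not its stated rule. But a term that decides arm membership should not be left to choice.

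On causality, Related has its own alternatives, including that the event is a known effect of the injection, and Section 2.3.1 lists precipitated withdrawal as a known XRNTX risk. A clinician could therefore grade it Related. This also stands, and it means that the rule supports two opposite grades for one event. Because that reaction is a listed risk, it would bear on the stopping rule mainly when serious.

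Safeguards exist. Withdrawal scales are scheduled during induction, suspected reactions to any study medication are reportable (Sections 2.3.1 and 8.3.6), and the stopping limb that compares arms is not worded by attribution. They protect data capture but do not settle the grading.

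A reader might go further in three ways that the documents do not support:

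- *That adverse event counting starts at the first injection.* Section 9.3 selects people and is not a time window. Section 8.3.1 covers the course of the study, so XRNTX participants who go on to injection keep their induction events.
- *That the relatedness rule removes events from the comparison between arms.* The summaries in Section 9.4.1 are all-cause.
- *That those who fail the naloxone challenge are lost from the XRNTX arm alone.* The challenge is required only for XRNTX, but the documents do not place it before or after randomisation.

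**Conclusion.** The causality point holds on the text. Sections 8.3.3.2 and 8.3.3.3 are tied to the injection, conflict with the study treatment wording that follows them, and allow the main expected reaction to be graded differently by arm. The consequence is a possible undercount of related XRNTX events, including for the attribution limb of the stopping rule.

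The analysis-set point holds only as an ambiguity. It rests on reading study drug as the extended-release products, and on applying Section 9.3 to the safety analysis. Section 9.4.1 does not say so, but no other set exists. It concerns only randomised XRNTX participants who never reach an injection.

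The size of any bias cannot be computed from the documents. The illustrative 1 to 14 points assumes 5-20% induction leavers and a risk in leavers above that in completers; at equal risk there is none. The primary endpoints are not affected. The correction should be made because the rule serves participant safety and costs little to put right.

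**What to change.** - **Sections 8.3.3.2 and 8.3.3.3:** replace injection with study treatment, defined as oral naltrexone, XRNTX, weekly or monthly XRBUP, and supplemental Suboxone.
- **Section 9.3:** define the safety set as all randomised participants who took at least one dose of any assigned induction or maintenance medication, including oral naltrexone.
- **Section 9.4.1:** state that the safety analysis uses this set, and that participants who leave during induction or are replaced under Section 7.2 stay in it.

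The cost is a few sentences, adverse event follow-up of participants who stop during induction, and slightly more analysis. No new data item, visit or design change is needed, because Sections 8.3.5 and 8.3.6 already require every adverse event in the study period to be recorded.
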